4.2.2 Secondary Outcome Measures

Measurement of secondary outcomes will occur using the instruments in the table below.

Measure	Study Objective	Time Point
Absolute Worth and Autonomy Scale	Aim 2b: Reducing distress among PCSO	Baseline, Waitlist Condition, Post Intervention, 8 Week FU, 12 Week FU
Perceived Stress Scale	Aim 2b: Reducing distress among PCSO	Baseline, Waitlist Condition, Post Intervention, 8 Week FU, 12 Week FU
Conflict Behavior Questionnaire	Aim 2b: Reducing distress among PCSO	Baseline, Waitlist Condition, Post Intervention, 8 Week FU, 12 Week FU
SCORE-15 Index of Family Functioning	Aim 2b: Reducing distress among PCSO	Baseline, Waitlist Condition, Post Intervention, 8 Week FU, 12 Week FU
Parenting Self Agency	Aim 2b: Reducing distress among PCSO	Baseline, Waitlist Condition, Post Intervention, 8 Week FU, 12 Week FU
Family Questionnaire	Aim 2b: Reducing distress among PCSO	Baseline, Waitlist Condition, Post Intervention, 8 Week FU, 12 Week FU
Motivational Interviewing Skills Questions	Aim 2a: Feasibility	Baseline, Post- Intervention
Mental Health Service Use History	Aim 2a: Facilitating engagement of IP in treatment	Baseline
Past Month Service Use History	Aim 2a: Facilitating engagement of IP in treatment	Baseline, Waitlist Condition, Post Intervention, 8 Week FU, 12 Week FU
Change Questionnaire	Aim 2b: Reducing distress among PCSO	Post Intervention, 12 Week FU

10 Minute Audio Recorded Role Play	Aim 2a: Feasibility	Baseline, Waitlist Condition, Post Intervention
------------------------------------	---------------------	---

5 Study Design

[figure not shown]
The study population is parents and concerned significant others (PCSO) of individuals experiencing psychosis (IP) who are not currently engaged with treatment. The IP has to have a recent onset of psychosis within the past 5 years. MILO is a structured brief intervention that seeks to accomplish two aims. The primary aim is to facilitate the engagement of IP with evidence-based treatments. The secondary aim is to reduce the distress and increase the wellbeing of PCSO. The intervention will be trialed for feasibility and then tested against a small waitlist condition control arm. Participants will be randomly assigned to either receive MILO (50%) or the waitlist condition (50%) in a cross over design.

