7.1 Subject Inclusion Criteria

In order to be eligible to participate in this study, an individual must meet all of the following criteria:

- PCSO is 18 years or older
- PCSO is able to communicate in English
- PCSO is a primary care giver or an individual who has ≥20 hours weekly contact with an IP
- PCSO is able to provide informed consent by demonstrating that they understand the aims and structure of the study

Although the individual with psychosis will not participate in MILO, study staff will establish via the participating PCSO that the individual with psychosis is:

- Aged 15-35
- Has been diagnosed with a DSM-5 psychotic disorder by a health professional, OR has clearly observable (by the PCSO) symptoms/behaviors indicating psychosis
- Experienced onset of observed symptoms or first psychosis diagnosis occurred within past five years
- Is not optimally engaged in outpatient treatment

Identifiable information about the individual with psychosis is not kept in study records. The information gathered about the IP is based on participants' reporting and perceptions.

Subject Exclusion Criteria

An individual who meets any of the following criteria will be excluded from participation in this study:

- Current mental health crisis: if study staff determine that the potential participant is in serious emotional distress during the eligibility determination and consent process, staff will consult with the PI to determine whether the participant should be referred to psychiatric care to address their distress prior to participating in MILO

8 Study Intervention

The active intervention includes four to five 45-60 minute sessions. Sessions will be conducted individually with the clinician, or if two or more PCSO (e.g., parents) wish to participate together, they will meet at the same time with the clinician. The first two sessions will focus primarily on teaching through concept review, demonstration, and role play. In the third and fourth sessions, the clinician will learn about PCSOs' efforts to initiate a conversation about treatment with the IP using, and will provide feedback, problem-solving, and encouragement regarding the PCSO's

efforts. A fifth session may be offered upon request to provide additional coaching, consultation, and psychoeducation relevant to MILO topics. See Table 1 for details about session content.

Session	Content

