11.1 Study Hypotheses

1. The MILO intervention will be feasible and acceptable for participants.
2. The MILO intervention will impact outcomes of interest (e.g., proficiency using MILO skills, confidence, stress, caregiving attitudes, and caregiver-reported IP treatment engagement).
3. Participants attending MILO sessions will show more improvement with regard to outcomes of interest within the first six weeks of study participation relative to those on the waitlist.
4. After attending MILO sessions, waitlisted participants will “catch up” to those randomized to receive the intervention immediately with regard to changes on outcomes of interest.
5. Gains in MI proficiency as demonstrated via scored audio recordings will mediate the impact of the intervention on other outcomes such as reduced conflict and stress and increased confidence and caregiver-reported IP treatment engagement.

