11.3 Statistical Methods

Feasibility will be analyzed using the following descriptive metrics: # participants screened; # Eligible; # Enrolled; # not enrolled and corresponding reasoning # Meeting DSM-5 Adjustment Disorder criteria; Percentage of Treatment sessions completed; Treatment Satisfaction; % assessments completed; Duration of assessments.

The outcomes of interest will be compared between the intervention and waitlist groups, and also within the waitlist group (comparing the pre-post intervention changes to the pre-post waitlist time changes. Prevalence of IP treatment seeking in each group will also be analyzed via odds ratios. Secondary outcomes, i.e. changes in PCSO distress and quality of life, will be

assessed via repeated measures ANOVAs examining group-by-time changes. Similarly, hypothesized mediators of effects (MI skill proficiency and self-efficacy) will be examined via repeated measures ANOVAs examining group-by-time changes. Analyses will be conducted using SPSS software.

12 Ethics/Protection of Human Subjects

This study is to be conducted according to applicable US federal regulations and institutional policies (which are based in federal regulations, guidance, and ICH Good Clinical Practice guidelines).

This protocol and any amendments will be submitted to the Boston Medical Center and Boston University Medical Campus IRB, for formal approval of the study conduct. The decision of the IRB concerning the conduct of the study will be made in writing to the investigator. A copy of the initial IRB approval letter will be provided to the sponsor before commencement of this study.

All subjects for this study will be provided a consent form describing this study and providing sufficient information for subjects to make an informed decision about their participation in this study. The consent form will be submitted with the protocol for review and approval by the IRB. The consent of a subject, using the IRB-approved consent form, must be obtained before that subject is submitted to any study procedure. Consent will be documented as required by the IRB.

13 Literature References

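### Hypothesis 5 claims mediation, but section 11.3 tests only whether the mediators change by group; the randomised comparison of continuous caregiver outcomes could also be made more precise by adjusting for the baseline score

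*Combined protocol and SAP*

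**What the plan says.** Section 11.1, hypothesis 5: "Gains in MI proficiency as demonstrated via scored audio recordings will mediate the impact of the intervention on other outcomes". The outcomes named there are conflict, stress, confidence and caregiver-reported treatment engagement of the individual with psychosis (IP).

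Section 11.3 gives the mediators one analysis: "hypothesized mediators of effects (MI skill proficiency and self-efficacy) will be examined via repeated measures ANOVAs examining group-by-time changes". The continuous caregiver outcomes are likewise to be "assessed via repeated measures ANOVAs examining group-by-time changes". Engagement is handled apart: "Prevalence of IP treatment seeking in each group will also be analyzed via odds ratios". Section 11.3 also plans a comparison between the intervention and waitlist groups, and a within-waitlist comparison of change over the intervention with change over the wait.

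Hypothesis 3 sets the window for the randomised comparison: "within the first six weeks of study participation relative to those on the waitlist". Under section 5 the immediate arm has four assessments and the waitlist arm five, the extra one falling at the end of the wait. The role play is scored at entry, end of waitlist and post-intervention.

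Section 8 expects some caregivers of the same IP to take part jointly: "if two or more PCSO (e.g., parents) wish to participate together, they will meet at the same time with the clinician".

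**The concern.** A stated hypothesis has no analysis that could support or refute it. In the planned ANOVA the mediator is the dependent variable. A significant result says that MILO teaches the skill. It does not say whether the skill is what lowers stress or conflict. Because section 11.3 calls these variables mediators and offers nothing else, a positive skill result could be reported as support for hypothesis 5.

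The second matter is efficiency. Section 11.2 accepts that the study may be somewhat underpowered and wants from it a rough effect size for a later full trial. The width of the interval around that estimate therefore matters, and the planned test does not make the best use of baseline scores that are already collected.

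**Working it through.** **Figures in the plan.** Section 11.2 gives 48 + 52 = 100 participants, which adds up. The plan states no alpha, power, effect size, SD or correlation, so the target of 100 cannot be derived or refuted by a formula.

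**Mediation.** Write a for the effect of arm on skill, b for the effect of skill on outcome given arm, and a × b for the indirect effect.

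| Quantity | Needed for hypothesis 5 | In section 11.3 |
|---|---|---|
| a (arm to skill) | yes | yes, mediator ANOVA |
| total effect of arm on outcome | context | yes, outcome ANOVA or odds ratio |
| b (skill to outcome, given arm) | yes | no |
| a × b with an interval | yes | no |

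The mediator F statistic is computed from arm and skill alone. The outcome does not enter it, so its distribution is the same whatever b is. A significant a together with a significant total effect still leaves b = 0 possible.

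**Limit of any indirect-effect estimate.** In the randomised period, skill and outcome are measured at the same visit. Suppose b = 0, MILO raises skill by 0.8 SD, and a common cause gives skill and outcome a residual correlation of 0.3 with equal residual SDs. The regression then returns a false b of 0.3 and a false indirect effect of 0.8 × 0.3 = 0.24 SD. In simulation with 50 per arm and r = 0.5, a bootstrap interval excluded zero in about 85% of such trials. All these inputs are assumptions.

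**Precision.** With two visits, the group-by-time F test is the t test on change scores. Take outcome SD 1 at both visits and baseline-to-follow-up correlation r:

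- change-score variance: 2(1 − r)
- baseline-adjusted variance: 1 − r²
- ratio: (1 − r²) / [2(1 − r)] = (1 + r)/2

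The ratio does not depend on sample size or allocation. Adjustment costs one degree of freedom.

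**Power, as illustration.** Assumed: d = 0.5, two-sided 0.05, equal arms of n, independent participants, no dropout. Noncentrality is 0.5 / √(V × 2/n). At r = 0.5:

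- n = 50, change score: 0.5/√(1.00 × 0.04) = 2.50, 98 df, power 70%
- n = 50, adjusted: 0.5/√(0.75 × 0.04) = 2.89, 97 df, power 82%
- n = 30, change score: 0.5/√(1.00 × 0.0667) = 1.94, 58 df, power 48%
- n = 30, adjusted: 0.5/√(0.75 × 0.0667) = 2.24, 57 df, power 59%

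| r | V change | V adjusted | ratio | power, 50 per arm | power, 30 per arm |
|---|---|---|---|---|---|
| 0.3 | 1.40 | 0.91 | 0.65 | 55% to 74% | 36% to 51% |
| 0.5 | 1.00 | 0.75 | 0.75 | 70% to 82% | 48% to 59% |
| 0.7 | 0.60 | 0.51 | 0.85 | 89% to 93% | 69% to 76% |

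At r = 0.5 the 95% interval half-width falls from 0.40 to 0.34 SD with 50 per arm, and from 0.52 to 0.45 SD with 30.

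**Which visits.** Hypothesis 3 asks about the first six weeks against waitlist, the waitlist arm is assessed at the end of its six-week wait, and section 11.3 compares the two groups and refers to change over the wait. Read together, these imply MILO post-intervention against end of waitlist, though section 11.3 does not name the pair.

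**The case against.** The strongest reply is that this is a pilot with feasibility as its primary outcome, that it concedes limited power, and that a change-score test is a legitimate analysis. That stands: the planned test is valid, and the case for adjustment is efficiency alone. The gain is also modest when r is high (89% to 93% at r = 0.7 with 50 per arm). The variance identity covers a two-visit analysis, and section 11.3 does not say how many visits enter the ANOVA.

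It can also be said that section 11.3 only undertakes to examine the mediators and never says the ANOVA proves mediation. True, but hypothesis 5 does assert mediation and no other analysis addresses it, so the gap remains.

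Three stronger readings are tempting, and the documents do not support them.

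- A reader might infer that the ANOVA would use only the visits common to both arms, when both have had MILO at every follow-up, and so miss hypothesis 3. No section says so, and section 11.3 plans a comparison against the waitlist. Naming the visits is a clarification, not the correction of an error.
- A reader might take all 100 participants as randomised. Sections 5 and 11.2 describe a two-phase study with Phase 1 complete, and the randomised number is not given. Section 5 also states a 50:50 split while section 11.2 expects a small control group. The power values therefore do not describe this trial.
- A reader might put a number on the error caused by ignoring caregivers who attend together. The documents give neither the share of such caregivers nor their correlation, so no figure is justified.

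**Conclusion.** The point holds on two counts. First, hypothesis 5 cannot be supported by the analysis in section 11.3, which covers the first path of mediation only. This follows from the text and needs no assumption. Second, for continuous caregiver outcomes compared at two visits, adjusting for baseline would reduce the variance to (1 + r)/2 of the change-score variance, a fall of 35%, 25% or 15% at assumed r of 0.3, 0.5 or 0.7. That result assumes randomised arms and equal SD at the two visits. It does not extend to the odds-ratio analysis of IP engagement. The power gains rest on an assumed d, r and n. The change should be made, but the randomised comparison as planned is not invalid.

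**What to change.** 1. In section 11.3, replace the group-by-time ANOVA for the randomised comparison with ANCOVA or a mixed model of the MILO post-intervention versus end-of-waitlist value on arm and baseline score, and name those two visits. Apply it to measures that have both a baseline and an end-of-waitlist value. In section 4.2.2 the Change Questionnaire ("Post Intervention, 12 Week FU") and the MI Skills Questions ("Baseline, Post- Intervention") do not, so they cannot be analysed this way.
2. Allow for caregivers of the same IP who take part together, with a random family effect or cluster-robust standard errors.
3. Keep post-crossover visits for hypothesis 4 and the within-waitlist comparison.
4. For hypothesis 5, choose one of two courses. Either state that the mediator ANOVA shows only a change in skill and is not evidence of mediation. Or, for continuous outcomes, add an indirect-effect estimate with a bootstrap interval that resamples families: regress role-play score on arm and its baseline, then the outcome on role-play score, arm and both baselines. Label it exploratory, because mediator and outcome share a visit and a common cause can produce a false indirect effect. Under either course, say that mediation of IP engagement is untested unless a method for a binary outcome is added.

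The cost is SAP wording, a different SPSS procedure and, if chosen, one bootstrap analysis. The role play and the scales concerned are already scheduled at the visits needed. The downside is a little more analysis work and more modest claims about mediation.
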